5. TEST ARTICLE ALLOCATION AND MASKING

5.1. Test Article Allocation

This is a multi-site, partially-subject masked (control lens only) and randomized study. The study lenses will be worn in a bilateral and random fashion using a 2 treatment by 3 period (2×3) crossover design.

Permuted block randomization will be used to minimize the potential for treatment imbalance. A block size of two (2) sequences will be utilized. A computer-generated randomization scheme will be used to randomly assign subjects to one of the two possible lens wear sequences (TEST/CONTROL/CONTROL or CONTROL/TEST/TEST). The random scheme will be generated using the PROC PLAN procedure from SAS Software Version 9.4 or higher (SAS Institute, Cary, NC).

The study site must follow the randomization scheme provided and complete enrollment according to the randomization list and not pre-select or assign subjects. The randomized assignment of subjects will be performed at the first visit prior to the first fitting. The following must have occurred prior to randomization:

- Informed consent has been obtained
- Subject meets all the inclusion / exclusion criteria
- Subject history and baseline information has been collected

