14.4. Level of Statistical Significance

The primary and secondary hypotheses will be tested with a type I error of 5% individually.

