For the β coefficients, independent non-informative priors $N(0, 1000)$ will be used. For the variance of random effect of σ_{site}^2 an independent non-informative conjugate prior, inverse-gamma(0.001, 0.001) will be used. For Σ , non-informative conjugate priors inverse-wishart(3,S) will be used where S is a 3X3 variance-covariance matrix of y_{ijkl} . Starting values for the mean and variance of CLUE scores will be 60 and 400 (since standard deviation of CLUE is normalized to be 20), respectively. The Metropolis sampler algorithm as implemented in the SAS/STAT MCMC procedure will be used to estimate the posterior distribution of the unknown parameters. Inferences will be made based on the 95% posterior credible intervals for relevant parameters.

Hypothesis Testing

The null and alternative hypotheses for CLUE comfort non-inferiority of the Test lens relative to the control lens are as follows:

$$H_o: \frac{\beta_1 + \beta_2 + \beta_3}{3} \leq -5$$

$$H_A: \frac{\beta_1 + \beta_2 + \beta_3}{3} > -5$$

Non-inferiority will be declared if the lower bound of the 2-sided 95% credible interval of the difference between the Test lens and the control lens is greater than -5, i.e., $P(\frac{\beta_1 + \beta_2 + \beta_3}{3} > -5) \geq 0.975$. Superiority will be declared if the lower bound of the 2-sided 95% credible interval of the difference between the Test and Control lens is greater than 0, i.e., $P(\frac{\beta_1 + \beta_2 + \beta_3}{3} > 0) \geq 0.975$. Superiority will only be tested if non-inferiority is established.

Lens Fit Acceptance

Lens fit acceptance will be analyzed using a Bayesian Logistic regression random-effects model to estimate the proportion of subjects eyes wearing the Test lens having acceptable lens fitting. The regression model will include period, sequence of lens wear and first order carryover effect. Site, subject nested within site and eye within subject within site will be included in the model as random effects.

Let $y_{ijklm}=1$ if an acceptable lens fit is observed for eyes wearing the Test lens only and $y_{ijklm}=0$ otherwise for the m^{th} subject, from the l^{th} site, for the i^{th} eye in the j^{th} period using the k^{th} sequence.

$$Y_{ijklm} \sim \text{Binary } (p_{ijklm})$$

$$p_{ijklm} = \frac{\exp(\text{Numerator})}{1 + \exp(\text{Numerator})}$$

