$$\text{Numerator} = \beta_0 + \beta_1 \text{Lens}_{i[j,k]} + \beta_3 \text{period}_{j1} + \beta_4 \text{period}_{j2} + \beta_5 \text{sequence}_k + \beta_6 \text{Carry1}_{i[j,k]} + \gamma_1 + \delta_{m(l)} + \alpha_{j(m(l))}$$

We assume the random subject eye effects are i.i.d as $\alpha_{j(m(l))} \sim N(0, \sigma_{\text{eye/subject/site}}^2)$ for eye nested within subject within clinical site, the random effect for subject are i.i.d as $\delta_{m(l)} \sim N(0, \sigma_{\text{subject/site}}^2)$ for subject nested within clinical site and the random clinical site effects are i.i.d as $\gamma_m \sim N(0, \sigma_{\text{site}}^2)$ for $i=1, 2$ (eye), $j=1, 2, 3$ (period) $k=1, 2$ (Sequence) $l=1, \dots, 5$ (Site) $m=1, \dots, n_l$ (subject/site).

For the β coefficients, independent non-informative priors $N(0, 10000)$ will be used. For the variance of random effects of $\sigma_{\text{eye/subject/site}}^2$, $\sigma_{\text{subject/site}}^2$ and σ_{site}^2 , independent non-informative conjugate priors inverse-gamma (0.001, 0.001) will be used. The Metropolis-Hastings algorithm as implemented in the SAS/STAT 14.1 PROC MCMC procedure will be used to estimate posterior distributions of the unknown parameters. Inferences will be made based on the posterior credible interval for the relevant parameters.

Hypothesis Testing

With respect to Acceptable lens fit the null and alternative hypothesis for superiority is as follows:

$$\begin{aligned} H_0 &= p \leq 0.90 \\ H_1 &= p > 0.90 \end{aligned}$$

Where, p represents the proportion of subject eyes that achieve acceptable fit for the Test lens.

Success for acceptable fit will be declared if the lower bound of the 2-sided 95% credible interval of the proportion is greater than 0.90; i.e. $P(P > 0.90) \geq .975$.

Primary safety analysis:

Slit Lamp Findings

Grade 3 or higher slit lamp findings will be analyzed using a Bayesian Logistic regression random-effects model to compare the Test and Control lenses. The regression model will include baseline slit lamp findings, lens type, period, sequence of lens wear and first order carryover effect. Site, subject nested within site and eye within subject within site will be included in the model as random effects.

Let $y_{ijklmn}=1$ if a Grade 3 or higher SLF is observed and $y_{ijklmn}=0$ otherwise for the n^{th} subject, from the m^{th} site, assigned to the i^{th} study lens for the j^{th} eye in the k^{th} period using the l^{th} sequence.

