$$Y_{ijklmn} \sim \text{Binary}(p_{ijklmn})$$

$$p_{ijklmn} = \frac{\exp(\text{Numerator})}{1 + \exp(\text{Numerator})}$$

$$\begin{aligned} \text{Numerator} = & \beta_0 + \beta_1 \text{Lens}_{ij[k,l]} + \beta_2 \text{Baseline SLF}_1 + \beta_3 \text{period}_{k1} + \beta_4 \text{period}_{k2} + \\ & \beta_5 \text{sequence}_k + \beta_6 \text{Carry1}_{i[k,l]} + \gamma_m + \delta_{n(m)} + \alpha_{j(n(m))} \end{aligned}$$

We assume the random subject eye effects are i.i.d as $\alpha_{j(n(m))} \sim N(0, \sigma_{\text{eye/subject/site}}^2)$ for eye nested within subject within clinical site, the random effect for subject are i.i.d as $\delta_{n(m)} \sim N(0, \sigma_{\text{subject/site}}^2)$ for subject nested within clinical site and the random clinical site effects are i.i.d as $\gamma_m \sim N(0, \sigma_{\text{site}}^2)$ for $i=1,2$ (lens), $j=1, 2$ (eye) , $k=1, 2, 3$ (period) $l=1, 2$ (Sequence) $m=1, \dots, 5$ (Site) $m=1, \dots, n_m$ (subject/site).

In this model, the lens I will be determined by the period k and sequence l , therefore i is denoted as a function of j and k . We define $\text{Lens}_i=0$ for the Control lens and $\text{Lens}_i=1$ for the Test lens.

For the β coefficients, independent non-informative priors $N(0, 10000)$ will be used. For the variance of random effects of $\sigma_{\text{eye/subject/site}}^2$, $\sigma_{\text{subject/site}}^2$ and σ_{site}^2 , independent non-informative conjugate priors inverse-gamma (0.001, 0.001) will be used. The Metropolis-Hastings algorithm as implemented in the SAS/STAT 14.1 PROC MCMC procedure will be used to estimate posterior distributions of the unknown parameters. Inferences will be made based on the posterior credible interval for the relevant parameters.

Hypothesis Testing

The null and alternative hypothesis for Non-inferiority is as follows:

$$H_0: p = (p_{\text{Test}} - p_{\text{Control}}) \geq 0.05$$

$$H_A: p = (p_{Test} - p_{Control}) < 0.05$$

Where p represents the difference between the proportion of subject's eyes with Grade 3 or higher SLFs of the test group compare to the control group. Non-inferiority will be established if the upper limit of the 2-sided 95% credible interval is below 0.05, i.e. $P(p=p_{Test} - p_{Control} < 0.05 | y)=0.975$.

In the event that the number of Grade 3 or higher SLFs is too small Grade 2 or higher SLFs will be analyzed and tested as described above.

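### The lens-fit model carries terms that Test-only data cannot estimate, and no stated step turns its conditional probability into the proportion tested against 90%

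*Combined protocol and SAP*

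**What the plan says.** Lens fit (Section 14.5, Lens Fit Acceptance). The outcome is 1 "if an acceptable lens fit is observed for eyes wearing the Test lens only". The text says that "The regression model will include period, sequence of lens wear and first order carryover effect". The equation that follows also has a Lens term, giving six fixed coefficients (intercept, Lens, two period terms, Sequence, Carry) plus random effects for site, subject and eye. The fixed-effect priors are N(0, 10000). In the hypothesis, "p represents the proportion of subject eyes that achieve acceptable fit for the Test lens". The rule is: "Success for acceptable fit will be declared if the lower bound of the 2-sided 95% credible interval of the proportion is greater than 0.90".

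Slit lamp (same section). The test concerns the difference in the proportion of "eyes with Grade 3 or higher SLFs of the test group compare to the control group", against a 5% margin, from a logistic model with the same kinds of random effect.

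Elsewhere. Section 5.1 gives the sequences as "TEST/CONTROL/CONTROL or CONTROL/TEST/TEST". Section 14.2 plans fit on a true rate of 95% with correlations of 0.80 within subject and period and 0.50 across periods. For slit lamp it uses 0.50 and 0.30. It does not say whether these are correlations of the binary outcomes or of a latent scale. Section 2.3 makes every primary and secondary hypothesis a condition of success.

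**The concern.** Two things are missing between the fit model and the fit test.

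First, a model restricted to one lens cannot estimate a lens effect. In this design it cannot separate sequence and carryover from period either.

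Second, in a logistic model with random effects, the probability for an eye whose random effects are zero is not the proportion of eyes in the population. For acuity and comfort, Section 14.5 writes the tested quantity as an explicit function of coefficients. An analyst who carries that habit into the logistic models would test the wrong quantity.

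Fit and slit lamp are both must-pass endpoints. Two analysts who each follow the text could reach opposite conclusions on the 90% rule.

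**Working it through.** **1. The plan's own figure.** Table 7 gives 83% power for fit with 70 subjects. Simulated Test-only data had 35 subjects per sequence, two eyes, and 35×2×1 + 35×2×2 = 210 eye-periods, with a true rate of 0.95 and correlations 0.80/0.50. The Section 14.5 rule applied to p averaged over the random effects gives power of about 0.35 (binary correlations) or 0.47 (latent), so 83% was not reproduced. The nearest variants each depart from a stated input or from 70 as the total:
- 210 independent eye-periods, exact binomial test at nominal one-sided 0.05: 0.831.
- 140 subjects in total, latent correlations, the stated rule: 0.818.

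This does not show that 83% is wrong. The simulation's analysis model, the correlation scale and the number of assessments per eye are not given, and the column heading leaves total versus per-sequence open.

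**2. Rank.** The coding is the one stated for the comfort model (Test/Control/Control = 1; carryover 1 after Test), assumed here for fit. Period 3 is taken as the reference.

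| Test cell | Int | Lens | Per1 | Per2 | Seq | Carry |
|---|---|---|---|---|---|---|
| TCC, period 1 | 1 | 1 | 1 | 0 | 1 | 0 |
| CTT, period 2 | 1 | 1 | 0 | 1 | 0 | 0 |
| CTT, period 3 | 1 | 1 | 0 | 0 | 0 | 1 |

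Lens equals the intercept, Seq equals Per1, and Carry is the period-3 indicator, 1 − Per1 − Per2. The rank is 3 of 6; with the Control rows added it is 6 of 6. With three cells, no other coding can give a rank above 3. The three cell means are estimable.

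**3. If p were read as expit(β0+β1).** Suppose the three cell logits are known exactly, all at logit(0.95) = 2.944. Given the priors, the precision of β0+β1 is 1/20000 + 1/20000 + 1/10000 + 1/10000 = 0.0003, so the SD is 57.7 logits. The mean is 2.944 × 0.00025/0.0003 = 2.45. The 95% interval for p runs from about 0 to 1, and P(p > 0.90) is about 0.50. The 0.975 rule then fails whatever the data say.

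**4. If p were taken at random effects of zero.** With one total random-effect SD s, the population rate is the mean of expit(b + sZ), Z standard normal, and the conditional value is expit(b). On the latent scale s² = r/(1−r) × π²/3. On the binary scale s is solved so that the binary correlation is r at a 90% rate.

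| Scale, r | s | True 90% shows as | True rate that shows as 90% |
|---|---|---|---|
| Latent, 0.50 | 1.81 | 96.2% | 81% |
| Latent, 0.80 | 3.63 | 99.4% | 71% |
| Binary, 0.50 | 3.44 | 99.3% | 72% |
| Binary, 0.80 | 9.58 | >99.99% | 59% |

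**5. Effect on the rule.** Trials were simulated (500 to 2000 per setting) with the plan's priors and 120 subjects. Simplifications: a common Test-cell mean, no site effect, one assessment per eye per period.

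| True rate and correlations | Pass rate, p at zero random effects | Pass rate, p averaged over them |
|---|---|---|
| 0.90, 0.80/0.50 | 0.98-1.00 | 0.02-0.04 |
| 0.90, binary 0.2/0.1 | 0.50-0.54 | about 0.05 |
| 0.95, 0.80/0.50 | 1.00 | 0.57-0.63 (binary), 0.72-0.75 (latent) |

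**6. Slit lamp.** Take a true 6.5% versus 0.5%, a 6-point difference beyond the margin, evaluated at random effects of zero.
- Latent, r = 0.30 (s = 1.19): 3.82% − 0.25% = about 3.6 points.
- Latent, r = 0.50 (s = 1.81): 2.09% − 0.10% = about 2.0 points.
- Binary: the answer depends on the rate at which s is solved. The largest value, for r = 0.30 solved at 6.5% (s = 2.29), is 1.22% − 0.05% = about 1.2 points.

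All of these lie inside the 5-point margin.

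**The case against.** The strongest reply is that the plan names the right target. Section 14.5 describes p as a proportion of eyes, which is a population quantity, and nowhere sets random effects to zero or uses expit(β0+β1). Where it does spell out a probability, for lens preference in Section 14.7, it takes a mean. Computed that way, p rests on estimable cell means and the rule keeps its size. This stands. A reader might infer that the 90% test is unidentified or inflated as written, or that the plan never refers to a population rate; the documents support neither. The two failures also come from different readings: the coefficient reading blocks success, and only the zero-random-effects reading inflates it.

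The correlation scale is also fair ground. It is unstated, so the binary-scale figures alone cannot be called the plan's. The most extreme row (s = 9.58) would impose 0.80 across periods too, where Section 14.2 assumes 0.50. Yet the bias persists on the latent scale and at much weaker correlations.

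Section 14.3 promises a separate SAP that would override this text. It may settle the point; nothing in the available documents does.

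**Conclusion.** The concern holds in limited form. The fit predictor is mis-specified for Test-only data (rank 3 of 6), and the step from the conditional probability to the tested proportion is missing. Its separate coefficients, and any p built on β0+β1, are driven by the priors; the Test-cell means and their averages are not.

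The choice left open is decisive. At a true 90% with 120 subjects and the planned correlations, the rule passes in 98-100% of trials on the conditional reading and in 2-4% on the averaged one. The slit-lamp gap is of the same kind, without the rank defect: a 6-point excess would show as about 2.0-3.6 points (latent) or below about 1.2 (binary).

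These sizes rest on the comfort-model coding carrying over, on normal random effects as specified, and on the simplifications listed above. The slit-lamp figures are a direct calculation, not a simulated error rate.

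**What to change.** 1. In the fit model keep intercept, period and the random effects, and drop Lens, Sequence and Carry. Intercept and period already saturate the three Test cells. Alternatively, include Control rows so that all six terms are estimable. Make the text and equation agree.
2. In each posterior draw, compute p as the fit probability with the random effects integrated out, averaged over the Test cells with stated weights, and apply the 0.90 rule to that p. The weights matter: Section 7.2 assesses fit three times in period 1 (the fitting, Visit 2 and Visit 3) and twice in each later period. With equal allocation, weighting by assessment gives 3/7, 2/7, 2/7, against 1/3 each for equal cells. The model has no visit index, so it must also say how repeated assessments enter.
3. Compute the Test and Control slit-lamp proportions marginally in the same way, over the same periods and sequences.
4. Re-simulate the Table 7 fit power for this p, stating the correlation scale, and restate it if it falls below 83%.

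The cost is a few lines of specification and post-processing. The fit estimate will be less favourable than a conditional one, and the simplified simulations suggest power of about 0.57-0.75 at 120 completers. That should be settled before any data are seen.

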14.6. Secondary Analysis

Secondary efficacy analysis:

CLUE Overall Quality of Vision and Handling

CLUE Overall Quality of Vision and Handling will be analyzed and test in the exact same manner as CLUE Overall Comfort.

Secondary safety analysis:

Not Applicable

14.7. Other Exploratory Analyses

Other efficacy analysis:

Lens Preferences:

Lens preference items listed below will be analyzed separately using Bayesian multinomial models for nominal data.

The regression models will include lens wearing sequence, age and gender as fixed covariates when appropriate. Investigational site will be included as random effect if the variation across sites is not negligible.

Let $\mathbf{y}_{ijkl} = (y_{ijk1}, y_{ijk2}, y_{ijk3}, y_{ijk4})$ denote subject lens preference for the i^{th} subject from the j^{th} site with regard to the k^{th} preference item. Possible values of y_{ijkl} are: $y_{ijk1} = 1$ if the subject preferred the Test lens, 0 otherwise; $y_{ijk2} = 1$ if the subject preferred the Control lens, 0 otherwise; $y_{ijk3} = 1$ if the subject preferred both the Test and Control lenses, 0 otherwise and $y_{ijk4} = 1$ if the subject preferred neither Test nor Control lenses, 0 otherwise. The likelihood of \mathbf{y}_{ijkl} is constructed as follow:

$$\begin{aligned}
 Y_{ijkl} &\sim \text{Multinomial}(p_{ijkl1}, p_{ijkl2}, p_{ijkl3}, p_{ijkl4}) \\
 p_{ijkl} &= \theta_{ijkl} / \sum_m \theta_{ijkl} \\
 \log(\theta_{ijkl}) &= \mu_{0kl} + \beta_{1k} \text{Sequence}_{ij} + \beta_{2k} \text{Age}_{ij} + \beta_{3k} \text{Female}_{ij} + \delta_j,
 \end{aligned}$$

where μ_{0kl} are the intercepts with μ_{0k4} set to 0, $p_{ijkl} = P(Y_{ijkl} = 1)$ and $\gamma_j \sim N(0, \sigma_s^2)$. We will use independent vague $N(0, 1000)$ priors for the regression coefficients μ_{0kl} , β_{1k} , β_{2k} and β_{3k} , and $IG(0.001, 0.001)$ for σ_s^2 .

Hypothesis Testing:

For each preference item, the null and alternative hypotheses for superiority are as follows:
 Ho: $OR_k \leq 1$ Ha: $OR_k > 1$; where OR_k represents the odds ratio of comparing the Test lens to the Control lens with regard to item k. The odds ratio is calculated as:

[figure not shown]
$$OR_k = p_{.k1}(1 - p_{.k2})/p_{.k2}(1 - p_{.k1}),$$

where $p_{.kl}$ is the mean estimate p_{ijkl} for $k=1, \dots, 5$ and $l = 1, \dots, 4$.

For each item k, the superiority will be declared if the lower bound of the 2-sided 95% credible interval of OR_k is greater than 1: $Pr(OR_k > 1 | y) \geq .975$.

Outdoor Glare Reduction

Outdoor Glare reduction consists of 4 individual questionnaire items.

All outdoor glare items are assessed using the same ordinal scale (1=Excellent ... 5=Poor). Outdoor Glare reduction items will be analyzed separately using a Bayesian multinomial model for ordinal data adjusting for baseline. The regression model will include sequence of lens wear, lens type, period and first order carryover effect. Clinical site and subject nested within clinical site will be included as random effects. Other subject characteristics such as age, gender, race and iris category will be included when appropriate.

The Model:

Let $y_{ijklm} = (y_{ijklm1}, y_{ijklm2}, y_{ijklm3}, y_{ijklm4}, y_{ijklm5})$ denote the rating for the m^{th} subject, from the l^{th} site, assigned to the i^{th} study lens in the j^{th} period using the k^{th} sequence. Possible values of y_{ijklm} are 1 if the subject rating of outdoor glare items are X and 0 otherwise (X=1 for Excellent and X=5 for Poor, respectively). The likelihood is constructed as follows:

$$y_{ijklm} \sim \text{Multinomial}(P_{ijklm1}, P_{ijklm2}, P_{ijklm3}, P_{ijklm4}, P_{ijklm5})$$

$$P_{ijklm1} = \gamma_{ijklm1}$$

$$P_{ijklmX} = \gamma_{ijklmX} - \gamma_{ijklm(X-1)} \quad 2 \leq n \leq 4$$

$$P_{ijklm5} = 1 - \sum_{x=1..4} P_{ijklmX}$$

$$\text{Logit}(\gamma_{ijklm}) = \theta_n + \beta_1 \text{Lens}_{i[j,k]} + \beta_2 \text{Period}_{j_1} + \beta_3 \text{Period}_{j_2} + \beta_4 \text{Sequence}_k + \beta_5 \text{Carry}_{i[j,k]} + \gamma_l + \delta_{m(l)}$$

Where θ_n is the intercept for levels $n=1,2,3,4$, $P_{ijklm1} = \Pr(\gamma_{ijklm1} = 1)$ with respect to outdoor glare preference. We assume the random subject effects are independent identically distributed (i.i.d) as $\delta_{m(l)} \sim N(0, \sigma_{subject/site}^2)$ for subject m nested within clinical site l and the random clinical site effects are i.i.d as $\gamma_l \sim N(0, \sigma_{site}^2)$ for $i=1,2$ (lens), $j=1, 2, 3$ (Period) $k=1, 2$ (Sequence) $l=1, \dots, 5$ (Site) $m=1, \dots, n_l$ (subject/site).

In this model, the lens i will be determined by the period j and sequence k , therefore i is denoted as a function of j and k . We define $Lens_i=0$ for the Control lens and $Lens_i=1$ for the Test lens. The odds ratio for having higher rating can be written as $OR=e^{-\beta_1}$.

Independent vague $N(0, 1000)$ priors for the regression coefficients β_i $i=1,\dots,5$. For θ_n , we are considering the following priors

$$\begin{aligned}\pi_0(01) &\sim N(0, 100) \\ \pi_0(02 | 01) &\sim N(0, 100)I(\theta > 01) \\ \pi_0(03 | 02) &\sim N(0, 100)I(\theta > 02) \\ \pi_0(04 | 03) &\sim N(0, 100)I(\theta > 03)\end{aligned}$$

For the variance of random effects independent vague normal priors will also be used; $\sigma_p^2 \sim \text{inverse-gamma}(0.001, 0.001)$ and $\sigma_s^2 \sim \text{inverse-gamma}(0.001, 0.001)$. The Metropolis sample algorithm as implemented in the SAS/Stat MCMC Procedure will be used to estimate the posterior distributions of the unknown parameters. Inferences will be made based on the posterior credible interval for the relevant parameters.

Hypothesis Testing

The null and alternative hypotheses for superiority are as follows:

$$H_0 \text{ } OR \leq 1$$

$$H_A \text{ } OR > 1$$

Where OR represent the odds ratio of having higher rating of the Test lens compared to the Control lens. Superiority will be declared if the lower bound of the 2-sided 95% credible confidence interval is above 1, i.e. $P(OR=e^{-\beta_1}>1|y)=0.975$.

Indoor Glare Reduction

Indoor Glare reduction consists of 4 individual questionnaire items:

Each item will be analyzed individually and tested in the exact same manner as the Outdoor Glare Reduction Items described above.

Driving Measures

Driving measure consists of two individual questionnaire items:

Each item will be analyzed individually in the exact same manner as the Outdoor Glare Reduction Items described above. However the hypothesis test will be as follows:

Hypothesis Testing

The null and alternative hypotheses for superiority are as follows:

$$H_0 \text{ } OR \leqslant 0.67$$

$$H_A \text{ } OR > 0.67$$

Where OR represent the odds ratio of having higher rating of the Test lens compared to the Control lens. Non-inferiority will be declared if the lower bound of the 2-sided 95% credible confidence interval is above 0.67, i.e. $P(OR = e^{-\beta_1} > 0.67 | y) = 0.975$. Superiority will be declared if the lower bound of the 2-sided 95% credible interval is above 1, i.e. $P(OR = e^{-\beta_1} > 1 | y) = 0.975$. Superiority will only be tested in the event that non-inferiority is established.

Other safety analysis:

Not Applicable

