2.2. Endpoints

Primary Endpoints

The primary endpoints are as follows:

Biomicroscopy

Biomicroscopy will be assessed for each subject eye at all study visits (scheduled and unscheduled). The percentage of Grade 3 or higher slit lamp findings will be analyzed and will include corneal infiltrates.

Distance Monocular Contact Lens Visual Acuity

Distance monocular contact lens visual performance (logMAR) is assessed for each subject eye at the 2-week follow-up evaluation.

Fit Acceptance Rate

Acceptable lens fit will be assessed at all scheduled visits for each subject eye. Fit acceptance rate will be based on the lens fit acceptance of eyes wearing the Test lens only. Fit rates of the control lens will also be collected, but are not a primary endpoint.

CLUE Overall Comfort

Overall comfort scores are assessed using the Contact Lens User Experience (CLUE) questionnaire at the two-week follow-up. CLUE is a validated patient-reported outcomes questionnaire to assess patient-experience attributes of soft, disposable contact lenses (comfort, vision, handling, and packaging) in a contact-lens wearing population in the US, ages 18-65. Scores follow a normal distribution with a population average score of 60 (SD 20), where higher scores indicate a more favorable/positive response. (2016)¹.

Secondary Endpoints

The Secondary endpoints are as follows:

CLUE Overall Quality of Vision and Handling

Overall Quality of vision and handling scores are assessed using the Contact Lens User Experience (CLUE) questionnaire at the 2-week follow-up. CLUE is a validated patient-reported outcomes questionnaire to assess patient-experience attributes of soft, disposable contact lenses (comfort, vision, handling, and packaging) in a contact-lens wearing population in the US, ages 18-65. Scores follow a normal distribution with a population average score of 60 (SD 20), where higher scores indicate a more favorable/positive response (2016)¹.

Other Observations

Lens Preferences

Lens preferences will be assessed by patient reported outcome (PRO) questions regarding lens preference at the 2-week follow-up of the second wearing period. Subjects will be asked to choose for each preference item one of the following responses: Strongly Prefer the first lens, Prefer the first lens, no preference, prefer the second lens, strongly prefer the second lens. Lens preference questions consist of:

[REDACTED]

Driving Performance

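### In the exploratory lens-preference model the covariates and site effect cancel from the probabilities, and the modelled classes do not match the answers offered; the expected effect on the odds ratio is small

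*Combined protocol and SAP*

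**What the plan says.** Section 2.2 (Other Observations, Lens Preferences) defines the data. For every item the subject picks a single answer from this list: "Strongly Prefer the first lens, Prefer the first lens, no preference, prefer the second lens, strongly prefer the second lens". That is one choice per item from five, with one tie answer.

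Section 14.7 (Lens Preferences) defines the model, a Bayesian multinomial for nominal data with four classes: Test preferred, Control preferred, a third class equal to 1 "if the subject preferred both the Test and Control lenses", and a fourth equal to 1 "if the subject preferred neither Test nor Control lenses". The fourth class has its intercept fixed at 0.

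On adjustment, Section 14.7 states: "The regression models will include lens wearing sequence, age and gender as fixed covariates when appropriate". It adds: "Investigational site will be included as random effect if the variation across sites is not negligible". The log weight of each class is written as "\mu_{0kl} + \beta_{1k} \text{Sequence}_{ij} + \beta_{2k} \text{Age}_{ij} + \beta_{3k} \text{Female}_{ij} + \delta_j", and a class probability is that class's weight divided by the sum of the weights.

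Superiority on an item needs a posterior probability of at least 0.975 that OR_k exceeds 1. Section 2.3 hypothesises superiority on all 5 items, under Other Observations.

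**The concern.** There are two separate faults.

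First, the classes and the answers do not correspond. Both and neither cannot be answered, and no preference has no class. Nothing says whether the strong and plain preferences are merged. Someone would have to choose the coding of ties later, possibly with the data in view.

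Second, in the log weight only the intercept has the class index l. The coefficients β_1k, β_2k and β_3k have only the item index k, and the site effect has only the site index. A term that is the same for every class cannot shift probability from one class to another. A report could then describe preference results as adjusted for sequence, age, gender and site when no adjustment took place.

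At stake is whether a pre-specified model with a formal superiority rule fits its own data and does what its text says.

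**Working it through.** The documents give no sample size, power or expected rate for lens preference (Table 7 in Section 14.2 does not list it), so there is no plan figure to reproduce. The check is algebra plus examples with assumed values.

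**1. Cancellation.** Let η = β_1k × Sequence + β_2k × Age + β_3k × Female + site effect, the same for every class. Then

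p_l = exp(μ_l + η) / Σ_m exp(μ_m + η) = exp(η) exp(μ_l) / [exp(η) Σ_m exp(μ_m)] = exp(μ_l) / Σ_m exp(μ_m).

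η has gone. With assumed intercepts 0.8, 0.4, −0.5 and 0, the weights are 2.226, 1.492, 0.607 and 1 (sum 5.324), and the probabilities are 0.418, 0.280, 0.114 and 0.188. With OR_k = p_1(1 − p_2) / [p_2(1 − p_1)] as in Section 14.7, OR_k = 1.85. Four different combinations of sequence, age, gender and site effect gave these same values to six decimals.

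For 120 simulated subjects with a real sequence effect, the log-likelihood was −149.76465038 at β_1k = −50, −5, 0, 5 and 50. A flat likelihood leaves each coefficient at its N(0, 1000) prior, SD √1000 = 31.6 if 1000 is the variance.

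**2. A more generous reading.** Suppose the whole log weight of the neither class, not just its intercept, is 0. Then η moves neither against the other three classes. As η runs from −2 to 2, OR_k moves from 1.61 to 1.98, but p_Test / p_Control stays at exp(0.8 − 0.4) = 1.4918. The balance between Test and Control is still unadjusted for sequence.

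**3. What a class index changes.** With assumed sequence coefficients of +0.7 for Test, −0.7 for Control and 0 otherwise, the probabilities in the second sequence become 0.656, 0.109, 0.089 and 0.146. The model can then represent an order effect. The size is illustrative only.

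**4. Classes.** One tie answer can fill at most one of the two tie classes. Assume 50 Test, 40 Control and 30 no preference among 120, fitted with the stated intercept priors:

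| Coding of ties | Empty class | Intercepts | OR_k |
|---|---|---|---|
| Neither | Both | both: −27.7 (SD 18.3) | median 1.43, 95% interval 0.74 to 2.80 |
| Both | Neither (the reference) | all three near 17 (SD 10.4) | median 1.43, 95% interval 0.73 to 2.80 |
| Dropped | Both and neither | – | (50/40)² = 1.56 |

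The raw value with ties kept is (50/70)/(40/80) = 1.43. With ties dropped, the log odds ratio is 2 ln 1.25 = 0.446 with SE 2√(1/50 + 1/40) = 0.424, an approximate 95% interval of 0.68 to 3.59. All three intervals include 1.

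**5. Size of any order bias.** Assume 60% of subjects prefer the later lens, no true preference and no ties. With 60 subjects per sequence the Test share is (60 × 0.6 + 60 × 0.4)/120 = 0.50 and OR_k = 1.00. With a 65/55 split it is (39 + 22)/120 = 0.508 and OR_k = (61/59)² = 1.07. The SE of log OR_k is about 2√(1/(120 × 0.25)) = 0.37, so the shift of ln 1.07 ≈ 0.067 is about 0.18 SE.

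**The case against.** The best defence is that the missing index is drafting shorthand. The block has other notational slips: the site effect is δ in the formula and γ in its distribution, for example. Against this, the sentence on priors also gives the intercepts the class index and the coefficients none, so the written model is consistent in leaving it out. Shorthand is likely, but the text as it stands specifies no adjustment.

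The defence is stronger on consequences, and most of it stands:

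- Covariates enter only when appropriate, and site only if its variation matters. But the written likelihood contains no information on the coefficients or the site variance, so this model could not inform either decision.
- A reader might infer that lens order will bias the comparison enough to produce a false claim. The documents do not support that. Coding the outcome as Test or Control already requires conversion by sequence, and Section 5.1 randomises in blocks of two sequences, so order is nearly balanced. A 65/55 split would need all ten losses between about 130 randomised and 120 completing to fall in one sequence. The comparison of lens 1 with lens 2 is made at Visit 4 (Section 7.2, step 4.5), so losses in the third period do not affect it.
- A reader might also infer that the intercepts are necessarily measured against an empty class. That is so only if ties are not coded as neither, which is a natural coding. In any case the decision uses OR_k, not the intercepts.
- Section 14.3 announces a separate SAP that overrides these sections, and the questionnaire in Appendix A is not shown. The actual coding and answer wording cannot be checked. If the form did offer both and neither, Sections 2.2 and 14.7 would still disagree.

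**Conclusion.** The point holds as a fault in specification. Read as written, the preference model makes no adjustment for sequence, age, gender or site; this is exact and needs no assumption. Its four classes do not match the five answers in Section 2.2, and at least one class must be empty.

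The expected effect on OR_k is small. Under the assumed 50/40/30 counts, coding ties as both or as neither leaves it at 1.43. Dropping them gives 1.56, still with an interval that includes 1. An extreme loss pattern with a 60/40 order tendency gives 1.07 in place of 1.00. These figures rest on assumed rates, since the documents give none.

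The analysis is exploratory. Section 2.3 ties the study objective to the primary and secondary hypotheses only, so no primary or secondary conclusion depends on this model. The correction is still worth making, because a formal superiority rule on five items is attached to it.

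**What to change.** In the lens-preference part of Section 14.7, or in the separate SAP:

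1. State that first-lens and second-lens answers are converted by sequence to Test, no preference or Control, and that strong and plain preferences are merged. Remove the both and neither classes.
2. Give the sequence, age, gender and site effects a class index, with all effects of the reference class set to 0. Use one symbol for the site effect.
3. Compute OR_k from class probabilities averaged over subjects and over the two sequences.

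An ordinal model that keeps all five levels, or a particular choice of reference class, is optional.

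The cost is a few sentences of model text and a few lines of code. No new data are needed.
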